4.3.1.2 Labeling of Serial Blood Samples

Serial blood samples will be labeled in a similar fashion, except that the collection timing will be labelled by week number (e.g. week 0 = pretreatment; week 8; week 16)

4.4 Detailed Patient Assessments

Subject assessments (physical examinations, vital signs, performance status, chemistry, hematology, medication review, and adverse event evaluations) will be conducted at screening, Cycle 1 Day 1, every 2 weeks thereafter until the first response assessment at 8 weeks, and then every 4 weeks thereafter. Study visits and the on-treatment tumor biopsy may be performed 3 days before or after the scheduled date due to unforeseen or unavoidable circumstances, and attempts should be made to schedule visits to line up with the start of a new cycle (within the constraints of the above parameters). Study drugs will be dispensed at the last visit prior to the start of the next 28 day cycle. The radiologic first response assessment at 8 weeks, and subsequent radiologic response assessments every 8 weeks thereafter, may be performed up to 7 days before or after the scheduled date due to unforeseen or unavoidable circumstances. Details are provided in Table 5, and a checklist highlighting the important events for screening through the completion of the trial is provided below, as Table 6.

4.4.1 Physical Examinations

A complete physical examination will be performed at the screening visit, on Cycle 1 Day 1, then every 2 weeks up to the first response assessment at 8 weeks, then every 4 weeks thereafter. Any significant physical examination findings after the administration of the first doses of LEE011 and everolimus will be recorded as adverse events. Body weight will be recorded during every physical exam. The subject will wear lightweight clothing and no shoes during weighing. Weight will be measured on the same scale at each visit. Height will be measured at the screening visit only; the subject will not wear shoes.

4.4.2 Medical History

At each visit, the subject's medical history will be reviewed and any changes from baseline will be recorded as an adverse event. On Day 1, any changes observed from the screening assessments, prior to dosing, will be recorded in the subject's medical history. All medications (prescription or over-the-counter, including vitamins and/or herbal supplements) will be recorded beginning with the screening visit and continuing up through the date of the final visit.

4.4.3 Vital Signs

Vital sign determinations of body temperature (in degrees Celsius), heart rate, respiratory rate, blood pressure and pain (using a 0-10 Numeric Ranking Scale) will be obtained at the screening visit, on each day the subject is seen by the treating physician, and at the final visit. If possible, blood pressure and heart rate measurements should not immediately follow scheduled blood collections.

4.4.4 Clinical Laboratory Tests

All subjects will undergo the laboratory assessments outlined in Table 5.

- 1) A complete blood count (CBC) with differential will be collected at the screening visit, on Cycle 1 Day 1, Cycle 1 Day 15, then every 2 weeks until the first response assessment, at the first response assessment at 8 weeks, then every 4 weeks thereafter.
- 2) Serum chemistries (total protein, albumin, total bilirubin, AST, ALT, alkaline phosphatase, sodium, potassium, chloride, bicarbonate, BUN, creatinine, calcium, magnesium, and phosphorous) will be collected at the screening visit, on Cycle 1 Day 1, Cycle 1 Day 15, then every 2 weeks until the first response assessment, at the first response assessment at 8 weeks, then every 4 weeks thereafter.
- 3) PT/PTT/INR will be collected at the screening visit, on Cycle 1 Day 15, and at final visit if the patient agrees to the optional third biopsy
- 4) Additionally, a tumor marker (serum CA19-9 or CEA level) and research blood samples for ctDNA will be sampled on Cycle 1 Day 1 and every 8 weeks thereafter.

Laboratory samples for this study will be assessed using the certified laboratory at the investigators' institutions, or at a clinical laboratory such as Quest or LabCorp and these data will

be used for all data analysis. The Principal Investigator or sub-investigator will review, initial and date all laboratory results. Any laboratory value outside the reference range that is considered clinically significant by the investigator will be followed as appropriate. Clinically significant laboratory values will be recorded as adverse events if they meet the criteria as specified in Section 8.

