2.6.1.1 RB, defined as positive if any tumor cells have RB nuclear staining

2.6.1.2 pRB, defined as positive if any tumor cells have phosphorylated-RB nuclear staining

2.6.1.3 p16, defined as positive if there is positive nuclear staining in 5% or more of tumor cells

2.6.1.4 Cyclin D1, defined as positive if any tumor cells have cyclin D1 nuclear staining

2.6.1.5 Ki67, defined as a percentage of positively stained cells (nuclear staining and mitotic figures) among the total number of malignant cells viewed in at least 3 randomly-selected high-power (x40 objective) fields

2.6.1.6 MCM7, defined as a percentage of positively stained cells (nuclei) among the total number of malignant cells viewed in at least 3 randomly-selected high-power (x40 objective) fields

2.6.1.7 pS6, defined using a histoscore of intensity and percent of tumor cells staining

2.6.2 Frequency of mutations (including, for example, *KRAS*, *CDKN2A*, *SMAD4*, and *TP53*) in the initial biopsy specimen from targeted NGS analyses from pre-treatment and on-treatment biopsy specimens

2.6.3 Frequency of mutations (including, for example, *KRAS*, *CDKN2A*, *SMAD4*, and *TP53*) from ctDNA as measured by quantitative PCR collected as detected in 5mL of serial blood samples collected every 8 weeks

2.7 Indication:

Patients with mPAC who have progressed on 5-FU- and GEM-based chemotherapy

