4.4.5 Collection and Processing of ctDNA

For collection of ctDNA on Cycle 1 Day and every 8 weeks thereafter, 4 mL of patient blood will be collected via venipuncture (venipuncture is preferred, however if an indwelling catheter must be used, 3 catheter volumes of blood must be collected and discarded prior to collection of the sample) into 2 evacuated Streck tubes. Immediately after collection, the tubes will be inverted 8 to 10 times to ensure good mixing of blood and placed in an ice bath. The date and time of collection for each sample will be recorded. The complete process of centrifugation, transfer to polypropylene tubes and freezing should be accomplished within 60 minutes from blood draw. The processing of samples should be performed as described below:

1. Immediately invert the collection tubes 8 to 10 times and placed in an ice bath.
2. Centrifuge the sample at 1,200 *g* for 10 minutes at 4°C to separate the plasma.
3. Isolate supernatants in sterile 1.5 mL Eppendorf tubes and centrifuge at 1,600 *g* for 10 minutes at 4°C
4. Transfer supernatants (plasma) using plastic pipettes into screw-capped polypropylene tubes labeled with the patient number, the protocol number, and the study week.
5. Store samples at –20°C or colder and ship on dry ice to [name] to:

Roswell Park Comprehensive Cancer Center
c/o [name]
[name]
[name]

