4.4.12 Protocol Deviations

The investigator should not implement any deviation from the protocol without prior review and agreement by the Sponsor and in accordance with the IRB and local regulations, except when necessary to eliminate an immediate hazard to study subjects.

Table 7. Study Activities

	Screening Visit	Cycle 1, Day 1	Cycle 1, Day 15	Every 2 Weeks thereafter until 1st Response Assessment	Cycle 2, Day 1	First Response Assessment (at 8 Weeks)	Every 4 Weeks after 1st Response Assessment	Every 8 Weeks after 1st Response	Off Study	Follow-up Assessments ^g
Informed consent	X									
Demographics	X									
Medical history	X	X	X	X	X	X	X	X	X	
Concurrent meds	X	X	X	X	X	X	X	X	X	
β-hCG	X ^a	X ^a								
Vital signs	X	X	X	X	X	X	X	X	X	
Height	X									
Weight	X	X	X	X	X	X	X	X	X	
History and physical	X	X	X	X	X	X	X	X	X	
Performance status	X	X	X	X	X	X	X	X	X	
Adverse event evaluation	X	X	X	X	X	X	X	X	X	
CBC w/ diff.	X	X	X	X	X	X	X	X	X	
Serum chemistry ^b	X	X	X	X	X	X	X	X	X	
Tumor markers ^c	X	X			X	X		X	X	
Radiologic evaluation and tumor measurements ^d	X					X		X	X ^h	
PT/PTT	X ^e		X ^e							
Tumor biopsy	X		X							
Research serum sample for ctDNA	X	X					X		X ⁱ	
Electrocardiogram (EKG) ^f	X									
Dispense study medications		X			X	X	X	X		
Survival		X	X	X	X	X	X	X	X	X

^aUrine or serum pregnancy test (women of childbearing potential)
^bAlbumin, alkaline phos., total bili., bicarbonate, BUN, calcium, chloride, creatinine, glucose, potassium, total protein, AST, ALT, sodium, phosphorus, magnesium
^cTumor marker (CA 19-9 or CEA)
^dScreening scans should be within 3 weeks of starting treatment
^eFor biopsy
^fElectrocardiograms should be done in triplicate, reviewed by the investigator, and confirmed by cardiology
^gUp to 24 months
^hUnless performed within 4 weeks of the off study date
ⁱOptional

Table 8. Study Activities Checklist

Screening

Subject assessment	_____
Eligibility criteria met	_____
Informed consent	_____
Demographics	_____
Medical History	_____
Concurrent medications	_____
ECG	_____
Pregnancy test (if appropriate)	_____
Vital signs	_____
Height	_____
Weight	_____
History and physical	_____
Performance status	_____
CBC with differential	_____
Serum chemistries	_____
PT/PTT/INR	_____
Radiologic Assessment	_____
Tumor amenable to biopsy	_____
Pre-treatment biopsy	_____

Cycle 1, Day 1

Subject assessment	_____
Concurrent medications	_____
Pregnancy test (if appropriate)	_____
Vital signs	_____
Weight	_____
History and physical	_____

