Performance status	_____
Adverse event evaluation	_____
CBC with differential	_____
Serum chemistries	_____
Serum Tumor Marker	_____
Research serum sample for ctDNA	_____
Dispense study drugs	_____

Cycle 1, Day 15

Subject assessment	_____
Concurrent medications	_____
ECG	_____
Vital signs	_____
Weight	_____
History and physical	_____
Performance status	_____
Adverse event evaluation	_____
CBC with differential	_____
Serum chemistries	_____
PT/PTT/INR	_____
On-treatment tumor biopsy	_____

Cycle 2, Day 1

Subject assessment	_____
Concurrent medications	_____
ECG	_____
Vital signs	_____
Weight	_____
History and physical	_____
Performance status	_____
Adverse event evaluation	_____
CBC with differential	_____
Serum chemistries	_____
PT/PTT/INR	_____
Serum Tumor Marker	_____
Dispense study drugs	_____

Every 2 weeks until first response assessment

Subject assessment	_____
Concurrent medications	_____
Vital signs	_____
Weight	_____
History and physical	_____
Performance status	_____
Adverse event evaluation	_____
CBC with differential	_____
Serum chemistries	_____

First response assessment (at 8 weeks on treatment)

Subject assessment	_____
Concurrent medications	_____
Vital signs	_____
Weight	_____
History and physical	_____
Performance status	_____
Adverse event evaluation	_____
CBC with differential	_____
Serum chemistries	_____
Serum Tumor Marker	_____
Radiologic Assessment	_____
Research serum sample for ctDNA	_____
Dispense study drugs	_____

Every 4 weeks after first response assessment

Subject assessment	_____
Concurrent medications	_____
Vital signs	_____
Weight	_____
History and physical	_____
Performance status	_____
Adverse event evaluation	_____
CBC with differential	_____
Serum chemistries	_____
Dispense study drugs	_____

Every 8 weeks after first response assessment

Subject assessment _____
Concurrent medications _____
Vital signs _____
Weight _____
History and physical _____
Performance status _____
Adverse event evaluation _____
CBC with differential _____
Serum chemistries _____
Serum Tumor Marker _____
Radiologic Assessment _____
Research serum sample for ctDNA _____
Dispense study drugs _____

Upon disease progression or off study

Subject assessment _____
Concurrent medications _____
Vital signs _____
Weight _____
History and physical _____
Performance status _____
Adverse event evaluation _____
CBC with differential _____
Serum chemistries _____
Serum Tumor Marker _____
Radiologic Assessment _____

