8.3 Analysis of ctDNA

ctDNA will be collected from patient serum at Cycle 1 Day 1 and every 8 weeks thereafter. Mutations identified by the targeted sequencing will be evaluated in the circulating DNA specimens using PCR (predominantly focused around KRAS, TP53, or *CDKN2A* mutations). We will correlate changes in the ctDNA abundance with PFS and tumor marker levels. The data will determine if ctDNA may be a possible surrogate marker for disease burden.

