9.4.2.5.1 RB, defined as positive if any tumor cells have RB nuclear staining

9.4.2.5.2 pRB, defined as positive if any tumor cells have phosphorylated-RB nuclear staining

9.4.2.5.3 p16, defined as positive if nuclear staining in 5% or more of tumor cells

9.4.2.5.4 Cyclin D1, defined as positive if any tumor cells have cyclin D1 nuclear staining

9.4.2.5.5 Ki67, defined as a percentage of positively stained cells (nuclear staining and mitotic figures) among the total number of malignant cells viewed in at least 3 randomly-selected high-power (x40 objective) fields

9.4.2.5.6 MCM7, defined as a percentage of positively stained cells (nuclei) among the total number of malignant cells viewed in at least 3 randomly-selected high-power (x40 objective) fields

9.4.2.5.7 pS6 (Ser235/236) defined using a histoscore of intensity and percent of tumor cells staining

9.4.2.6 Frequency of mutations from targeted NGS analyses from pre-treatment biopsy specimens will be ranked.

9.4.2.7 ctDNA will be collected via serial blood samples with frequency as described above and quantitatively measured, defined as the number of mutant fragments in 5 mL by quantitative PCR.

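### Table 7's ctDNA row contradicts the every-8-weeks schedule given elsewhere and leaves out the week-8 draw; the ctDNA volume and sample type also differ between sections

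*Combined protocol and SAP*

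**What the plan says.** **Timing in the text and in Table 8.** Section 4.4.4 gives the tumor marker and ctDNA one shared schedule: "research blood samples for ctDNA will be sampled on Cycle 1 Day 1 and every 8 weeks thereafter". Section 8.3 repeats it: "ctDNA will be collected from patient serum at Cycle 1 Day 1 and every 8 weeks thereafter". Section 4.4.5 has the same interval, and 2.6.3 defines the exploratory endpoint "as detected in 5mL of serial blood samples collected every 8 weeks". The labeling rule in 4.3.1.2 (repeated in 8.1.1.2) gives as its example "week 0 = pretreatment; week 8; week 16". The Table 8 checklist lists a ctDNA sample under the heading "First response assessment (at 8 weeks on treatment" and again every 8 weeks after that visit. It also lists one at progression or off study, with no optional mark; the biopsy line just below is marked optional.

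**Timing in Table 7.** The row "Research serum sample for ctDNA" is marked at Screening, at Cycle 1 Day 1, in the column for every 4 weeks after the first response assessment, and at Off Study with a footnote making it optional. The first-response (week 8) and every-8-weeks cells are blank.

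**Volume and sample type.** Section 4.4.5 says that "4 mL of patient blood will be collected via venipuncture", into two tubes, and the processing steps keep the plasma. Section 9.4.2.7 has ctDNA "quantitatively measured, defined as the number of mutant fragments in 5 mL by quantitative PCR", without naming a sample type. Section 2.6.3 says 5 mL of blood. Section 8.3 and Tables 7 and 8 say serum.

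**The concern.** Table 7 is an operational schedule. Section 4.4.4 itself sends the reader to the study activities table for the laboratory assessments, under an outdated number: it says Table 5, which is now a list of concomitant medications. The section with the every-8-weeks rule therefore also points sites to the table that contradicts it. A week-8 blood sample that is not taken cannot be recovered.

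The loss would be selective. Section 8.3 plans to correlate change in ctDNA with PFS and with tumor marker levels, and to judge whether ctDNA could be a surrogate for disease burden. That needs post-baseline values in patients who do badly as well as in those who do well. If change is measured mainly in patients who passed the week-8 scan, the early-progression end of the PFS range is largely missing. The week-8 tumor marker, which Table 7 does mark, would have no ctDNA sample beside it.

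The volume and sample-type conflict is a separate matter. A fragment count has a meaning only for a stated volume of a stated material, and the sections do not agree on either.

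**Working it through.** The plan gives no sample size, power or error rate for ctDNA, so there is no figure to reproduce. The check compares the schedules and then counts the patients affected.

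**1. Table 7 row.** The table has ten columns and the ctDNA row has ten cells.

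| Column | ctDNA, Table 7 | Tumor marker, Table 7 | ctDNA, 4.4.4 and Table 8 |
|---|---|---|---|
| Screening | marked | marked | no |
| Cycle 1 Day 1 | marked | marked | yes |
| Cycle 1 Day 15 | blank | blank | no |
| Every 2 weeks to week 8 | blank | blank | no |
| Cycle 2 Day 1 | blank | marked | no |
| Week 8 | **blank** | marked | **yes** |
| Every 4 weeks after | **marked** | blank | **no** |
| Every 8 weeks after | **blank** | marked | **yes** |
| Off study | optional | marked | Table 8: yes, no optional mark; 4.4.4: not mentioned |
| Follow-up | blank | blank | no |

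The radiology row also has ten cells, and its marks fall at screening, week 8, every 8 weeks and off study, as they should. A general column shift is therefore unlikely.

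**2. First on-treatment sample.** Under 4.4.4 and Table 8 it is week 8. Under Table 7 the first non-optional one is 8 + 4 = week 12. The every-4-weeks mark then covers weeks 12, 16, 20, 24 and so on, so weeks 16 and 24 are still sampled. The scheduled draw that is lost is week 8.

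**3. Patients affected if Table 7 is followed.** Inputs: 26 evaluable patients (3.1.2) and 8-week progression-free rates of 25% and 50% (9.5.1). Assumption: patients who are not progression-free at week 8 leave by then.

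- Only an optional post-baseline sample: 26 × (1 − 0.25) = 19.5 at the null rate; 26 × (1 − 0.50) = 13 at the alternative.
- Available for a week-12 sample: at most 26 × 0.25 = 6.5 and 26 × 0.50 = 13.

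**4. Volume.**

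- If 4 mL is the total, 4/5 = 0.80 of the stated 5 mL of blood is drawn. Expressing that count per 5 mL of blood needs a factor of 5/4 = 1.25.
- If 4 mL is per tube, 2 × 4 = 8 mL is drawn and 5 mL of blood is available.
- If the 5 mL in 9.4.2.7 meant plasma, then with plasma assumed to be 50–60% of blood, 4 mL yields 2.0–2.4 mL and 8 mL yields 4.0–4.8 mL. Neither reaches 5 mL.

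The documents do not say which case applies, and 4.4.5 does not ask for the plasma volume to be recorded.

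**The case against.** The strongest reply is that the week-8 draw is scheduled almost everywhere and Table 7 is the single outlier. That stands. A reader might infer that the protocol has no week-8 sample, or that the endpoint cannot be derived. The documents do not support either: a site that follows 4.4.4 or the Table 8 checklist collects what 8.3 needs. The patient counts above describe only what happens where Table 7 is followed instead.

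Other inferences also go too far:

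- **Early progressors would have no post-baseline sample.** Table 7 gives them an optional one, and Table 8 lists one without that qualification. The optional mark may even belong to the biopsy, which is the optional off-study item in Table 8 and has no off-study mark in the Table 7 row just above ctDNA. That is possible but not shown.
- **Only 3 or 9 of 26 would reach a week-12 sample.** This comes from a constant-hazard extrapolation: 26 × 0.25^1.5 = 3.3 and 26 × 0.50^1.5 = 9.2. Scans are 8-weekly and patients stay on study until progression is seen, so a patient who passes the week-8 scan normally attends week 12. Those figures are lower bounds; the upper bounds are 6.5 and 13.
- **Less than half of the required volume would be assayed.** This holds only if 5 mL means plasma. Section 2.6.3 says blood, and 9.4.2.7 does not say. A count can be rescaled, and a constant factor cancels in within-patient change. It cancels only if the plasma volume is constant or known.

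Finally, ctDNA is exploratory in 2.3, 2.6 and 9.5.2.5, with no test or decision rule. Its listing under the secondary endpoints heading in 9.4.2 does not change that. This limits the severity but does not remove the contradiction.

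**Conclusion.** The contradiction is real. Table 7 omits the week-8 ctDNA draw, substitutes an every-4-weeks schedule, adds a screening draw, and differs from Table 8 on whether the off-study draw is optional. The effect where a site follows Table 7 is about 19.5 of 26 patients (null) or 13 of 26 (alternative) with only an optional post-baseline sample. This rests on the assumption that patients not progression-free at week 8 have left by then, and on the Table 7 marks being as printed. The planned analysis of ctDNA change would then largely exclude early progressors.

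The volume and sample-type conflict (4 mL against 5 mL; plasma, serum and blood) is also real, but it leaves the count ambiguous rather than unmeasurable.

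Severity is minor to moderate. The point deserves correction because a missed sample is permanent and the correction is nearly free.

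**What to change.** 1. In Table 7, mark ctDNA at the first response assessment and in the every-8-weeks column, and remove the every-4-weeks mark. State that the week-8 sample is taken whatever the scan shows.
2. Reconcile the screening mark and the off-study draw between Table 7, Table 8 and 4.4.4. The schedule text does not require a compulsory off-study draw; whether to have one is the sponsor's choice, but the tables should agree.
3. Correct the outdated Table 5 references in 4.4 and 4.4.4 so that they point to the study activities table.
4. Use one sample type (plasma, as processed in 4.4.5) and one volume basis in 2.6.3, 4.4.5, 8.3 and 9.4.2.7, and change the sample name in Tables 7 and 8 to match. Copies per mL of plasma, with the plasma volume recorded for each sample, would serve.
5. Say in 4.4.5 whether 4 mL is the total or per tube.

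The cost is an amendment to one table row and some endpoint wording. Blood is already drawn for hematology and chemistry at the week-8 and off-study visits, so no extra visit is needed.

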4.4.5 Collection and Processing of ctDNA

For collection of ctDNA on Cycle 1 Day and every 8 weeks thereafter, 4 mL of patient blood will be collected via venipuncture (venipuncture is preferred, however if an indwelling catheter must be used, 3 catheter volumes of blood must be collected and discarded prior to collection of the sample) into 2 evacuated Streck tubes. Immediately after collection, the tubes will be inverted 8 to 10 times to ensure good mixing of blood and placed in an ice bath. The date and time of collection for each sample will be recorded. The complete process of centrifugation, transfer to polypropylene tubes and freezing should be accomplished within 60 minutes from blood draw. The processing of samples should be performed as described below:

1. Immediately invert the collection tubes 8 to 10 times and placed in an ice bath.
2. Centrifuge the sample at 1,200 *g* for 10 minutes at 4°C to separate the plasma.
3. Isolate supernatants in sterile 1.5 mL Eppendorf tubes and centrifuge at 1,600 *g* for 10 minutes at 4°C
4. Transfer supernatants (plasma) using plastic pipettes into screw-capped polypropylene tubes labeled with the patient number, the protocol number, and the study week.
5. Store samples at –20°C or colder and ship on dry ice to [name] to:

Roswell Park Comprehensive Cancer Center
c/o [name]
[name]
[name]

